9.1. Handling of missing data

The relevant item's definition at Chapter 10 or thereafter defines how to impute data. In addition, for date imputation, follow the table below to impute the dates.

Item	Entry data			Dates after imputation	Replacement
	year	month	day		
Chest X ray, Thoracic CT, other imaging, Tuberculin test, QuantiFeron test, endoscopy	2018	1	null	January 1, 2018	If a date is null, regard it as the first day of the month.
	2018	1	-97	January 1, 2018	If a date is unknown, regard it as the first day of the month.
	2018	1	The first 10 days of a month	January 1, 2018	If a date is any of the first 10 days of a month, regard it as the first day of the month.
CRP	2018	1	null	null	If the date is null, it is regarded as null.
	2018	1	The end of a month	January 31, 2018	If the date is “the end of month”, replace it with the actual end date of the applicable month.
CDAI	null	1	1	null	If a year is null, it is regarded as null.
General (including the items above and WPAI)	-97	-97	-97	null	If a year, a month and a date are all unknown, they are regarded as null.
	null	null	null	null	If a year, a month and a date are all null, they are regarded as null.
	2018	-97	-97	null	If a month and a date are unknown, they are regarded as null.
	2018	null	null	null	If a month and a date are null, they are regarded as null.

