Indication	If multiple checkboxes such as Crohn's disease or others are selected for indication in “1. Patient information” in the survey form, count the number for each indication. Note that Crohn's disease should be selected

Data name	Derivation and calculation methods
	to display the item of indication in Attachment Form 3.
Tuberculin test	Conducted :When the first administration date of Humira is 1 and a day before the first administration date is -1, the patients who underwent Tuberculin test between -90 and 1 are regarded as the patients with Tuberculin test. Of note, the data in the survey form shall be used. Not conducted: other than the above
QuantiFeron test	Conducted: When the first administration date of Humira is 1 and a day before the first administration date is -1, the patients who underwent QuantiFeron test between -90 and 1 are regarded as the patients with QuantiFeron test. Of note, the data in the survey form shall be used. Not conducted: other than the above
Chest X ray test	Conducted: When the first administration date of Humira is 1 and a day before the first administration date is -1, the patients who underwent Chest X ray test between -90 and 1 are regarded as the patients with Chest X ray test. Of note, the data in the survey form shall be used.
Thoracic CT test	Conducted: When the first administration date of Humira is 1 and a day before the first administration date is -1, the patients who underwent thoracic CT scan between -90 and 1 are regarded as the patients with thoracic CT scan. Of note, the data in the survey form shall be used.
Imaging procedure	Conducted: When the first administration date of Humira is 1 and a day before the first administration date is -1, the patients who underwent chest X ray, thoracic CT scan, or other imaging tests between -90 and 1 are regarded as the patients with imaging test. Of note, the data in the survey form shall be used.
Tuberculosis test	The patients who underwent (Tuberculin test or QuantiFeron test) and (chest X ray, thoracic CT scan, or other imaging tests). Of note, the data in the survey form shall be used.
Patients subject to AAA measurement	Patients who are included in “CD Long AAA Measurement (final report).xlsx”.
Patients of contraindications	The patients whose registration form has at least a check on the checkbox of contraindications.
Patients who developed an infection	The patients with an infection in an external file “The priority survey item list_MedDRA20.1_FIX.xlsx”.

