12.2. Assessment period of endoscopy results

Time allowance of assessment period with the first administration date of Humira as 1 is as follows:

Assessment period	Time Allowance(Day)
At the first administration	- 1 (scheduled date 1)
Month 6 of administration	2 - 182 (scheduled date 183)
Year 1 of administration	183 - 364 (scheduled date 365)
Year 2 of administration	365 - 728 (scheduled date 729)
Year 3 of administration	729 - 1092 (scheduled date 1093)
At final assessment	Final assessment of each patient no matter whether the each assessment period is within Time Allowance.

The data for analysis should derive from the date closest to the scheduled date within Time Allowance. If there are more than one data dated on the same day, select the worst value.

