Note: Follow “12.2 Assessment period for endoscopy results” for Time Allowance of assessment period. The analysis covers only the patients with the data showing that endoscopy for small and large intestines was done on the same day at the first administration and thereafter in the effectiveness analysis group.

“3.2.6.2 Changes in WPAI:CD since the administration was started (Observed Case)”

Patients for analysis: patients in the effectiveness analysis group

Analysis objective: to show WPAI at each assessment period.

Analysis items: Calculate the number of target patients and the summary statistics of WPAI for each assessment period, and conduct a paired-t test which compares the values at the initial administration.

Note: Follow “12.1 Assessment period for CDAI, WPAI, CRP and non-intestinal conditions” for Time Allowance of the final assessment periods. The analysis covers only the patients with the WPAI assessment at the first administration and thereafter in the effectiveness analysis group.

“3.2.7.2 Changes in CRP level since the administration was started (Observed Case)”

Patients for analysis: patients in the effectiveness analysis group

Analysis objective: to show CRP levels at each assessment period.

Analysis items: Calculate the number of target patients and the summary statistics of CRP for each assessment period, and conduct a paired-t test which compares the values at the initial administration.

Note: Follow “12.1 Assessment period for CDAI, WPAI, CRP and non-intestinal conditions” for Time Allowance of the final assessment periods. The analysis covers only the patients with the CRP assessment at the first administration and thereafter in the effectiveness analysis group.

“3.2.7.3 Remission rate at the final assessment in patients who achieved a remission of CDAI at Week 4 of administration”

Patients for analysis: Patients in the effectiveness analysis group (the patients who did not achieve a remission (≥ 150) when the administration was started but achieved the remission (< 150) at Week 4 of administration in CDAI)

Patients for analysis: to show the remission rate of CDAI at the final assessment regarding the patients who did not achieve a remission (≥ 150) when the administration was started but achieved the remission (< 150) at Week 4 of administration.

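### SAP 9.1 sets a missing examination day to the 1st of the month without checking the first-dose date, so some on-treatment endoscopies and TB tests enter the pre-treatment windows and some endoscopy pairs pass as same-day.

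*SAP*

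**What the plan says.** The date table in SAP 9.1 has a block for "Chest X ray, Thoracic CT, other imaging, Tuberculin test, QuantiFeron test, endoscopy". Within it, "If a date is null, regard it as the first day of the month" and "If a date is unknown, regard it as the first day of the month". A loosely recorded early-month date goes the same way: "If a date is any of the first 10 days of a month, regard it as the first day of the month". Only a wider gap stops the imputation: "If a month and a date are unknown, they are regarded as null". SAP 9.1 allows Chapter 10 onwards to define its own imputation, but none is given there for these examination dates.

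Three later rules use the result:

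- **SAP 12.2, endoscopy.** The window for the first administration is printed with no lower limit, as a dash and then "1 (scheduled date 1". I read this as up to and including Day 1. The Month 6 window starts at Day 2. Within a window, the record nearest the scheduled day is used.
- **SAP 10.1, TB tests.** For example, "the patients who underwent QuantiFeron test between -90 and 1 are regarded as the patients with QuantiFeron test". Tuberculin, X-ray, CT and other imaging have the same window.
- **SAP 13.3, chart 3.2.5.3.** It is restricted to patients with data showing that "endoscopy for small and large intestines was done on the same day at the first administration and thereafter".

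**The concern.** The imputed day decides whether an examination counts as before or after treatment, yet the rule takes no account of when treatment started. The 1st of a month can never be later than a first dose given in that month. A missing-day record from that month therefore cannot be classed as post-dose, whatever actually happened.

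Post-dose records are expected. Protocol 8(3) item 12 collects endoscopy during treatment as well as at baseline, and item 8 collects examination days and imaging for tuberculosis or serious infection.

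At stake are the pre-treatment column of charts 3.2.4.2 and 3.2.5.2, the mean interval from pre-dose endoscopy to first dose in those charts, the pairing in chart 3.2.5.3, and tuberculosis-test status. That status is tabulated in chart 1.12 and tested as a background factor in charts 2.9 and 3.4.1. An error in it would not be visible, because SAP 11 gives it only two levels, conducted and not conducted.

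**Working it through.** **The plan's own example.** Year 2018, month 1, day null or unknown gives January 1, 2018. This reproduces.

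**Why a same-month record always lands before or on Day 1.** Let the first dose fall on day *d* of a month. A missing-day examination in that month is moved to the 1st, which is *d* - 1 days before the dose. With Day 1 as the first dose and no Day 0, the study day is 1 if *d* = 1 and 1 - *d* otherwise. The lowest possible value is 1 - 31 = -30. Every value lies at or below Day 1 and above Day -90, so it is inside both windows.

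**Worked case.** First dose 15 January, endoscopy 25 January, day missing.
- True study day: 25 - 15 + 1 = 11, in the Month 6 window (Day 2 to 182).
- Imputed: 1 January, Day -14, in the first-administration window.
- If the patient also has a dated endoscopy on 10 January (Day -5), that one is nearer Day 1 and is used.
- If the only other one is dated 1 November (75 days before dosing), the imputed record is nearer and displaces the real baseline.

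**Enumeration.** I took every first-dose date from 1 November 2011 to 31 October 2013 (the registration period, 731 days in 24 months, as a stand-in for first-dose dates) with every examination date in the same month.
- Pairs: 14×31² + 8×30² + 29² + 28² = 22,279.
- Examination after dose: (22,279 - 731)/2 = 10,774, or 48.4%.
- Of these, 10,774 (100%) are imputed to Day -29 to Day 1, inside both windows.

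The 100% follows from the rule. The 48.4% only describes evenly spread, independent dates and does not estimate the data.

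**By delay.** For a missing-day examination *k* days after the dose (*k* up to 28), the share still in the dose month is (731 - 24*k*)/731. At 7 days this is 563/731 = 77%; at 14 days, 395/731 = 54%. From 31 days on, the enumeration gives 0%. The problem is confined to about the first month.

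**Tuberculosis-test status.** SAP 10.1 requires (tuberculin or QuantiFeron) and (X-ray, CT or other imaging). One misdated image changes the status only if a skin or blood test also qualifies and no genuine pre-dose image exists. The same holds with the roles exchanged.

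**Same-day condition.** Two missing-day endoscopies in one month both become the 1st, so they match every time. With start dates spread evenly, 77% of pairs 7 days apart and 54% of pairs 14 days apart share a month and would pass as same-day if both days were missing.

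**Would another fixed day do?** For the same enumeration:

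| Imputed day | Post-dose called baseline | True pre-dose or Day 1 kept as baseline |
|---|---|---|
| 1st (SAP) | 100% | 100% |
| 15th | 28.4% | 78.1% |
| Month end | 0% | 6.4% |

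No single day recovers the order within the first-dose month.

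**The case against.** The strongest reply is that little may follow from this.

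- The closest-date rule can still select a real dated baseline, and the two-part TB definition blocks many single misdated tests. Both points stand. A reader might infer that every such record becomes the reported baseline or alters TB status; the documents support only that it enters the window.
- Charts 3.2.4.2, 3.2.5.2 and 3.2.5.3 give counts and percentages, and the first two also give mean days. None specifies a test against baseline. A reader might infer a biased effectiveness comparison, but the SAP plans no such endoscopy comparison. This stands.
- Malignancy, serious infection, CDAI, WPAI and CRP do not use the first-of-month rule; CRP with a null day is left null. This stands, and it also shows that the SAP already accepts leaving a date unresolved.
- The sponsor may query forms (Protocol 6(3) item 5), and the form may label endoscopies as baseline or during treatment (Protocol 8(3) item 12). This helps in part: the form is not available here, and the SAP does not tell the programmer to use such a label.
- The error does not always run one way. A tuberculin test on 25 October is 82 days before a 15 January dose. Moved to 1 October it is 106 days before, and counts as not conducted. With evenly spread dates, 10,774 of 66,521 in-window tests (16.2%) would be lost this way if the day were missing. The one-way error is therefore a statement about the first-dose month only.

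**Conclusion.** The point holds as a defect in a stated rule. In the first-dose month, a missing-day endoscopy, TB test or chest image cannot be classed as post-dose, and two missing-day endoscopies in one month cannot be classed as different days. Nothing later in the SAP overrides this. It rests on reading the endoscopy window as up to Day 1, which its scheduled day of 1 supports.

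The consequence is limited to the endoscopy charts 3.2.4.2, 3.2.5.2 and 3.2.5.3 and to tuberculosis-test status in charts 1.12, 2.9 and 3.4.1, under the conditions set out above. The size cannot be stated, because the documents give no count of missing days. It would be wrong to infer that about half of the partly dated examinations are misplaced: 48.4% applies only to first-dose-month pairs under even spread, and it would be lower if screening mostly precedes dosing. The change is worth making because it is cheap and replaces a rule that is known to misplace records.

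**What to change.** 1. **SAP 9.1.** Where the day is missing and the month is the first-dose month, use a baseline or pre-treatment label if the form records one. Otherwise class the timing as unknown and place the record in neither the baseline nor a post-dose window.
2. **SAP 10.1 and SAP 11.** Add an unknown level for tuberculosis-test status. SAP 9.2 already excludes unknowns from tests.
3. **Chart 3.2.5.3.** Require complete dates for both endoscopies before they count as same-day.
4. **Reporting.** Give the number of missing-day records by examination type and how many fall in the first-dose month.

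I do not propose mid-month imputation for the other months. In the October example, 15 October is 92 days before the dose, still outside Day -90. The loss of TB tests at the early edge of the window therefore remains, and item 4 would show whether it matters.

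The cost is SAP wording and programming, including the TB definitions and the stratification table. The downside is that a few true baseline records move to unknown, and some truly same-day endoscopy pairs with missing days leave chart 3.2.5.3.

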9.2. Descriptive statistics

The following will be calculated for categorial data and quantitative data.

Data type	Item to be calculated
Categorical data	
Number of patients, percentage, etc.
 
When the percentage is calculated, the number of patients of “unknown/not provided” is included in the denominator.
 
Chapter 13 stipulates the details regarding the setting of denominators.
 
The patients of “unknown” and “not provided” are excluded in the statistical test.

Quantitative data	Summary statistics: number of cases, mean, standard deviation, median, minimal value, maximal value, 1st quartile value, and 3rd quartile value

9.3. Display digit for figures

The display digit for figures is as follows:

Type of figure	Display digit
Mean, standard deviation, median, 1st quartile value, 3rd quartile value, 95% confidence interval	The figure in the significant digit + 2 digits of data is rounded off to the figure in the significant digit of data + 1 digit for display.
Minimal value, maximal value	The same number of digits is used for the significant digit of data.
Number of patients	Displayed as a whole number
Percentage	The figure is rounded off to the nearest one decimal place for display. When figures for Attachment Form 2, incidences of adverse events, etc are rounded off to two decimal places, the details are specified in the chart layout.
p value	Round the 5 decimal places down to the 4 decimal places. When the figure is smaller than 0.0001, display it as <0.0001 across the board.
Significant digit	The figure for duration of illness should be displayed with the significant digit rounded to the one decimal place. For others, the display digit of data should be the significant digit. As for CRP, the summary statistics except the number of patients should be rounded off to two decimal places.

9.4. Figure display rule

Case	Display rules
If a figure is incalculable	Hyphen “-”

9.5. Statistical test method

The test does not include the classification of unknown/not provided. In principle, the first layer is subjected to the intersegmental test of classified data. Multiplicity is not adjusted.

9.6. Significant level

In principle, the significant level is 5%, two-tailed. $p < 0.05$ ($< 5\%$) shall be considered significant.

10. Derivation and calculation methods for data

10.1. General

Data name	Derivation and calculation methods
Number of sites for this survey	Aggregate the number with DCF code.
The first administration date of Humira	It shall be the oldest date among the dates described in “the administration status of Humira” in the survey form.
The final administration date of Humira	
Do not use for analysis the record of the first administration date of Humira + 1092 days < the first administration date among the data described in “the administration status of Humira” in the survey form.
 
The final administration date of Humira shall be the most recent date among the final administration dates imputed in the following [1] to [4]:
 
[1] Sort data in the order of “the first administration date” of “the administration status of Humira”, dosing frequency and description.
 
[2] If the final date is provided, there is no check on the checkbox of “continued”, and the final administration date can be identified, select the date described as the final administration date.
 
If the final date is not described, the checkbox of “continued” is checked, and the final administration date cannot be identified, follow the below:
 
 • The final record: Impute the first administration date of Humira + 1092 days on the final administration date. • Other than the final record: Impute the first administration date of the next record - 1 day on the final administration date. 
[3] Even though the final dates are described, but the final administration date is incomplete and cannot be identified, follow the below:
 
 • If the year and month are described but the date is unknown, impute the final date of the month as the final administration date. • If the year is described and the month and date are unknown, impute the final date of the year as the final administration date. If the next record has already been generated and the first administration date of the next record comes earlier than the imputed date, impute the first administration date of the next

Data name	Derivation and calculation methods
	
record - 1 day for the final administration date.
 
Of note, if the final administration date is provided in the record where the final administration date of Humira has been identified according to the above rule and the “continued” checkbox is checked, follow the below:
 
 ● If the described final administration date > the final administration date imputed according to the above rule, select the imputed final administration date as the final administration date of Humira for the patient. ● If the described final administration date <= the final administration date imputed according to the above rule, select the described final administration date as the final administration date of Humira for the patient. 
If the first administration date of Humira + 1092 days < the final administration date of Humira imputed according to the above rule, select the first administration date of Humira + 1092 days as the final administration date of Humira.

Days to the final administration date of Humira	The final administration date of Humira - the first administration date of Humira + 1
Total exposure period (in years)	(Days to the final administration date of Humira + 28) / 364
Discontinued patients	
 • Patients whose final administration date of Humira comes before the first administration date of Humira + 1064 (Week 152) • Patients with a washout period with 60 days or longer. 
*The final administration date of Humira should be the administration date right before the washout of ≥ 60 days starts.

Reason for discontinuation	When a reason for discontinuation is described in the survey form, it is defined as ‘with’ reason for discontinuation. When no such description is found, it is defined as an “unknown/not provided”.
Death cases	At least a piece of data on “death” is found as the outcome of the adverse events during the safety analysis period.
Pediatrics	Patients aged < 15 years
The elderly	Patients aged ≥ 65 years

Data name	Derivation and calculation methods
Presence/absence of complications	When complication data are contained in the survey form, it should be classified as “with complications”. When the description in the survey form is not clear enough (when the check of with/without complications is not assessable or when multiple checkboxes are checked), it should be ‘unknown’ while no description should be ‘not provided’. Other cases are “no complications”.
Complication/Hepatic function disorder	When liver-disorder data are contained in “171210 Complications.xlsx”, it should be classified as “with hepatic function disorder”. When the description in the survey form is not clear enough (when the check of with/without complications is not assessable or when multiple checkboxes are checked), it should be ‘unknown’ while no description should be ‘not provided’. Other cases are “no hepatic function disorder”.
Complication/Renal impairment	When renal-disorder data are contained in “171210 Complications.xlsx”, it should be classified as “with renal impairment”. When the description in the survey form is not clear enough (when the check of with/without complications is not assessable or when multiple checkboxes are checked), it should be ‘unknown’ while no description should be ‘not provided’. Other cases are “no renal impairment”.
Complication/Blood disorder	When blood-disorder data are contained in “171210 Complications.xlsx”, it should be classified as “with blood disorder”. When the description in the survey form is not clear enough (when the check of with/without complications is not assessable or when multiple checkboxes are checked), it should be ‘unknown’ while no description should be ‘not provided’. Other cases are “no blood disorder”.
Complication/Respiratory disorder	When respiratory-disorder data are contained in “171210 Complications.xlsx”, it should be classified as “with respiratory disorder”. When the description in the survey form is not clear enough (when the check of with/without complications is not assessable or when multiple checkboxes are checked), it should be ‘unknown’ while no description should be ‘not provided’. Other cases are “no respiratory disorder”.
Complication/others	When other data are contained in “171210 Complications.xlsx”, it should be classified as “with others”. When the description in the survey form is not clear enough (when the check of with/without complications is not assessable or when multiple checkboxes are checked), it should be ‘unknown’ while no description should be ‘not provided’. Other cases

Data name	Derivation and calculation methods
	are “no others”.
Intestinal complications	
Classify the complications as mentioned in the presence/absence of intestinal-complications column of survey form.
 
Of note, if the presence/absence check is not assessable or multiple checkboxes are checked, it should be classified into ‘unknown’, while no description should be ‘not provided’.

Non-intestinal complications	
Classify the complications as mentioned in the presence/absence of non intestinal-complications column of survey form.
 
Of note, if the presence/absence check is not assessable or multiple checkboxes are checked, it should be classified into ‘unknown’, while no description should be ‘not provided’.

Presence/absence of medical history	
When medical-history data are contained in the survey form, it should be classified as “with medical history”. When the checkbox of ‘medical history unknown’ is checked, it should be ‘unknown’ while no description should be ‘not provided’. Others are “no medical history”.

Medical history: tuberculosis	
When medical-history data on tuberculosis are contained in “180111 medical history.xlsx”, it should be classified as “with medical history of tuberculosis”. When the checkbox of ‘medical history unknown’ is checked, it should be ‘unknown’ while no description should be ‘not provided’. Others are “no medical history of tuberculosis”.

Medical history: non-tuberculous mycobacteriosis	
When medical-history data on non-tuberculous mycobacteriosis are contained in “180111 medical history.xlsx”, it should be classified as “with medical history of non-tuberculous mycobacteriosis”. When the checkbox of ‘medical history unknown’ is checked, it should be ‘unknown’ while no description should be ‘not provided’. Others are “no medical history of non-tuberculous mycobacteriosis”.

Medical history: interstitial pneumonia	
When medical-history data on interstitial pneumonia are contained in “180111 medical history.xlsx”, it should be classified as “with medical history of interstitial pneumonia”. When the checkbox of ‘medical history unknown’ is checked, it should be ‘unknown’ while no description should be ‘not provided’. Others are “no medical history of interstitial pneumonia”.

Medical history: bronchitis bacterial	
When medical-history data on bronchitis bacterial are contained in “180111 medical history.xlsx”, it should be classified as “with medical history of bronchitis bacterial”. When the checkbox of ‘medical history unknown’ is checked, it should be ‘unknown’ while no description

Data name	Derivation and calculation methods
	should be ‘not provided’. Others are “no medical history of bronchitis bacterial”.
Medical history: aplastic anaemia	When medical-history data on aplastic anaemia are contained in “180111 medical history.xlsx”, it should be classified as “with medical history of aplastic anaemia”. When the checkbox of ‘medical history unknown’ is checked, it should be ‘unknown’ while no description should be ‘not provided’. Others are “no medical history of aplastic anaemia”.
Medical history: pancytopenia	When medical-history data on pancytopenia are contained in “180111 medical history.xlsx”, it should be classified as “with medical history of pancytopenia”. When the checkbox of ‘medical history unknown’ is checked, it should be ‘unknown’ while no description should be ‘not provided’. Others are “no medical history of pancytopenia”.
Medical history: malignant tumour	When medical-history data on malignant tumour are contained in “180111 medical history.xlsx”, it should be classified as “with medical history of malignant tumour”. When the checkbox of ‘medical history unknown’ is checked, it should be ‘unknown’ while no description should be ‘not provided’. Others are “no medical history of malignant tumour”.
Patients with an hepatitis B virus infection	“Hepatitis” “Hepatitis virus carrier” in “Complications” and/or “Medical history” of “1. Patient information” in the survey form → hepatitis viral infections. If “B” in “Complications” and/or “Medical history” is selected, classified the patients as those with hepatitis B virus infection. In addition, a patient with any events of MedDRA PT code provided in “Patients with hepatitis 180111B virus infection.xlsx” should be also classified as a patient with hepatitis B virus infection.
Presence/absence of administration of anti-hepatitis B virus agent	If the following drug codes are included in the survey form, regard the case as “with administration of an anti-hepatitis B virus agent”. Others are “without administration of an anti-hepatitis B virus agent”. Entecavir (Baraclude): 6250029 Tenofovir (Tenofovir, Viread): 6250024 Adefovir (Hepsera): 6250026 Lamivudine: 6250006, 6250020
Presence/absence of allergy history	When allergy data are contained in the survey form, it should be classified as “with allergy history”. When the checkbox of ‘medical history unknown’ is checked, it should be ‘unknown’ while no

Data name	Derivation and calculation methods
	description should be ‘not provided’. Others are “no allergy history”.
Presence/absence of smoking history	When the checkbox of ‘with’ smoking history is checked in the survey form, regard it as ‘with’ smoking history. When the checkbox of ‘no’ smoking history is checked in the survey form, regard it as ‘without’ smoking history. When the checkbox of ‘unknown’ for smoking history is checked in the survey form, regard it as ‘unknown’. If nothing is described in the survey form, it should be ‘not provided’.
Details of smoking history	For the items for smoking history in the survey form, when the ‘smoking’ checkbox is checked or when the smoking years column is checked of the ‘smoking’ checkbox, regard it as “smoking”. When smoking “in the past” is checked other than “smoking” or when the smoking years for “in the past” is provided, regard it as “only in the past”. When a case is not applicable to “smoking” or “only in the past” though a smoking history exists, regard it as “unknown”.
Administration status	
[1] 1st administration: as a patient with a dose of 160mg
 
[2] 2nd administration: 2nd administration date - the first administration date = 14 days \pm4 days or less, and a patient with a dose of 80mg.
 
[3] 3rd administration: 3rd administration date - the 2nd administration date = 14 days \pm4 days or less, and a patient with a dose of 40mg.
 
[4] 4th administration and thereafter: the dosing frequency “once every 2 weeks” is checked in the survey form, and a patient with a dose of 40mg
 
* If the patient receives the fourth administration and thereafter, all the administration status should be the condition as shown in [4].

	
If all the following [1] to [4] are satisfied, aggregate the data as “160mg \rightarrow 80mg \rightarrow 40mg once every two weeks”. Others are aggregated as “others”.
 
Of note, when data on administration status include only [1], [2] and [3] or when the data ends halfway for some reason, determine whether the case satisfies the criteria from [1] to [4] as of the final data on administration status, and classify it.

Data name	Derivation and calculation methods
Administration status (total number of dosing, total dose)	
 Dosing frequency 
[1] Sort data in the order of “the first administration date” of “the administration status of Humira”, dosing frequency and description.
 
[2] Calculate the dosing interval per data on administration status. “When “once every two weeks” is checked, regard it as a 14-day interval. For others, obtain the frequency from “dosing interval”.
 
[3] Calculate the dosing frequency per data on administration status. Dosing frequency = (the final administration date (the date imputed based on the definition of 10.1 Final administration date of Humira) – the first administration date(after imputed))/dosing frequency (number of days)
 
When the results of [4] and [3] are “>0” (bigger than 0) and “<1” (smaller than 1), count it as 1.
 
If the figure is “>=1” (1 or bigger), round the decimal down to the integer for the dosing frequency.
 
[5] The total number of dosing shall be the total of [4] per patient.
 Dose 
[1] When the dose of Humira is ‘others’, obtain the dose from “Dose_other description”.
 
[2] Calculate the dose per data of the administration status.
 
Dose = the number of dosing * a dose
 
[3] The total dose should be the total of [2] per patient.
 The mean of a dose 
The mean of a dose = the total dose/the total number of dosing

Patients with self-administration	The patients whose registration form has a check on self-administration.
Age	It should be identified based on the date of birth or the first administration date of Humira in the survey form. Of note, if the “date” of birth is incomplete and not provided, impute 1 as the date. When the date of birth is still incomplete even after the above imputation, just mirror the age provided in the survey form.
Indication	If multiple checkboxes such as Crohn's disease or others are selected for indication in “1. Patient information” in the survey form, count the number for each indication. Note that Crohn's disease should be selected

Data name	Derivation and calculation methods
	to display the item of indication in Attachment Form 3.
Tuberculin test	Conducted :When the first administration date of Humira is 1 and a day before the first administration date is -1, the patients who underwent Tuberculin test between -90 and 1 are regarded as the patients with Tuberculin test. Of note, the data in the survey form shall be used. Not conducted: other than the above
QuantiFeron test	Conducted: When the first administration date of Humira is 1 and a day before the first administration date is -1, the patients who underwent QuantiFeron test between -90 and 1 are regarded as the patients with QuantiFeron test. Of note, the data in the survey form shall be used. Not conducted: other than the above
Chest X ray test	Conducted: When the first administration date of Humira is 1 and a day before the first administration date is -1, the patients who underwent Chest X ray test between -90 and 1 are regarded as the patients with Chest X ray test. Of note, the data in the survey form shall be used.
Thoracic CT test	Conducted: When the first administration date of Humira is 1 and a day before the first administration date is -1, the patients who underwent thoracic CT scan between -90 and 1 are regarded as the patients with thoracic CT scan. Of note, the data in the survey form shall be used.
Imaging procedure	Conducted: When the first administration date of Humira is 1 and a day before the first administration date is -1, the patients who underwent chest X ray, thoracic CT scan, or other imaging tests between -90 and 1 are regarded as the patients with imaging test. Of note, the data in the survey form shall be used.
Tuberculosis test	The patients who underwent (Tuberculin test or QuantiFeron test) and (chest X ray, thoracic CT scan, or other imaging tests). Of note, the data in the survey form shall be used.
Patients subject to AAA measurement	Patients who are included in “CD Long AAA Measurement (final report).xlsx”.
Patients of contraindications	The patients whose registration form has at least a check on the checkbox of contraindications.
Patients who developed an infection	The patients with an infection in an external file “The priority survey item list_MedDRA20.1_FIX.xlsx”.
Patients who developed malignant tumour	The patients with malignant tumour in an external file “The priority survey item list_MedDRA20.1_FIX.xlsx”.
Duration of illness (in	“For XX years and XX months” should be converted into the figure in

Data name	Derivation and calculation methods
years)	
years for “duration of illness” of “patient information” in the survey form.
 
When both figures of year and month: year + month/12
 
When the figure of year is provided: year
 
When the figure of month is provided: month/12
 
Other cases are identified as “unknown/not provided” as the duration cannot be identified.

Concomitant medication	
Concomitant medications should the data satisfying the following rules:
 
When concomitant-medication data are contained in the survey form, it should be classified as “with concomitant medications”. When “presence/absence of anti-tuberculosis drug”, “presence/absence of concomitant medications” in the survey form are not assessable, select “unknown” while they are not provided, select “not provided”. Other cases are “without concomitant medications”.
 
◆ Data with a drug name in “administration status of anti-tuberculosis drug”, “concomitant medications” of the survey form
 
 When ‘from before Humira administration is started’ is checked, the first administration date should be the same as the first administration date of Humira”. When the year and month are described for the first administration date of the concomitant medication, impute “1” for the “date”. When the year is described for the first administration date of the concomitant medication, impute “1” each for the “month” and “date”. When ‘continued’ is checked, the final administration date should be the same as the final administration date of Humira. When the year and month are described for the final administration date of the concomitant medication, impute the month’s final date for the date. When the year is described for the final administration date of the concomitant medication, impute “12” for the month and “31” for the date. When the final administration of concomitant medication < the first administration date of Humira, and/or when the final administration date of Humira < the first administration date of concomitant

Data name	Derivation and calculation methods
